## 9.2 SAMPLE SIZE DETERMINATION

As specified in ANSI Z80.12:2007 (R2017) –C.4, a minimum of 300 subjects implanted with the investigational IOL and 150 subjects implanted with the comparator IOL must be available for analysis at Visit 5 (postoperative days 330-420). To consider the potential loss of subjects between the time of enrollment and study completion, a total of approximately 501 subjects will be randomized and undergo surgery in this study. It is assumed that of approximately 501 subjects who undergo surgery, 51 subjects (10%) will be discontinued prematurely or lost to follow-up. Subjects will be randomized to receive either the investigational or comparator IOL in a 2:1 ratio. Of 501 subjects who undergo surgery, approximately 334 subjects will receive the investigational IOL and 167 subjects will receive the comparator IOL. Expecting a screen failure rate of 7%, up to 539 subjects will be enrolled in the study to have 501 subjects randomized and scheduled for surgery.

For effectiveness, 300 subjects (first operative eyes) randomized to FINEVISION HP IOL and 150 subjects (first operative eyes) randomized to AcrySof SN60AT [REDACTED] IOL completing through Month 6 (Visit 4) yields >99% power to reject  $H_{01e}$  in favor of  $H_{11e}$  and conclude the FINEVISION HP IOL is non-inferior to the AcrySof SN60AT [REDACTED] IOL in BCDVA (logMAR) at Month 6 (Visit 4), using a one-sided test with an alpha level of 0.05 and assuming no difference in mean BCDVA between test and control IOLs, a common standard deviation of 0.10 logMAR, and a non-inferiority margin of 0.10 logMAR.

Similarly with the sample size required for safety, 300 subjects (first operative eyes) randomized to FINEVISION HP IOL and 150 subjects (first operative eyes) randomized to AcrySof SN60AT [REDACTED] IOL completing through Month 6 (Visit 4) will have >99% power to demonstrate superiority of FINEVISION HP IOL to AcrySof SN60AT [REDACTED] IOL in DCIVA (reject  $H_{03e}$  in favor of  $H_{13e}$ ) and DCNVA (reject  $H_{02e}$  in favor of  $H_{12e}$ ) using a two-sided test with an alpha level of 0.05 and assuming a true difference in means of -0.10 logMAR (FINEVISION HP minus AcrySof SN60AT [REDACTED] with a common standard deviation of 0.14 logMAR.

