### 5.1 Primary Effectiveness Variable Sample Sizes

#### 5.1.1 BEST CORRECTED DISTANCE VISUAL ACUITY

For effectiveness, 300 subjects (first operative eyes) randomized to FINEVISION HP IOL and 150 subjects (first operative eyes) randomized to AcrySof® SN60AT [REDACTED] IOL completing through Month 6 (Visit 4) yields greater than 99% power to reject  $H_{01e}$  in favor of  $H_{11e}$  and conclude the FINEVISION HP IOL is non-inferior to the AcrySof® SN60AT [REDACTED] IOL in BCDVA (logMAR) at Month 6 (Visit 4), using a one-sided t-test with an alpha level of 0.05 and assuming no difference in mean BCDVA between the IOLs, a common standard deviation (SD) of 0.10 logMAR, and a non-inferiority margin of 0.10 logMAR.

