## 5.3 Secondary Effectiveness Variable Sample Sizes

### 5.3.1 DISTANCE CORRECTED INTERMEDIATE VISUAL ACUITY

300 subjects (first operative eyes) randomized to FINEVISION HP IOL and 150 subjects (first operative eyes) randomized to AcrySof® SN60AT [REDACTED] IOL completing through Month 6 (Visit 4) will have more than 99% power to demonstrate superiority of FINEVISION HP IOL to AcrySof® SN60AT [REDACTED] IOL in DCIVA (reject  $H_{03e}$  in favor of  $H_{13e}$ ) using a two-sided t-test with an alpha level of 0.05 and assuming a true difference in means of -0.10 logMAR (FINEVISION HP minus AcrySof® SN60AT [REDACTED]) with a common SD of 0.14 logMAR.

[figure not shown]

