## **13. Effectiveness Analyses**

### **13.1 Primary Analyses**

The co-primary effectiveness endpoints are:

- Photopic monocular logMAR best corrected distance visual acuity (BCDVA) in first operative eyes at Month 6 (Visit 4)
- Photopic monocular logMAR near visual acuity with distance correction (DCNVA) in first operative eyes at Month 6 (Visit 4)

The primary analyses of the primary effectiveness endpoints will be based on the AAS with intercurrent events handled using the primary strategy presented in [Section 8.2](#).

If a subject has no observed data for an endpoint at any of the scheduled visits (e.g. subject exits study prior to Month 1 [Visit 3A] study visit and therefore has no DCNVA data), the endpoint will be imputed at the earliest scheduled visit as a normal random variable with mean equal to the respective treatment group mean and SD equal to the respective treatment group SD based on observed data for the respective treatment group at the earliest scheduled visit for that endpoint. If the imputed value is less than the minimum observed value within the respective treatment group or greater than the maximum observed

value within the respective treatment group, the imputed value will be set equal to the minimum or maximum value, respectively. This initial imputation procedure will be performed for BCDVA using SAS® code similar to the code below:

```

proc means data = indata noprint;
  var base;
  by trt;
  output out = A3_stats(drop = _TYPE_ _FREQ_) mean = mean std
= sd min = min max = max;
run;

data indata(drop = mean sd min max Z);
  call streaminit(938428);
  merge indata indata_stats;
  by trt;

  if cmiss(base, aval_v2, aval_v3, aval_v4, aval_v5) = 5 then
do;
  Z = round(rand('Normal', mean, sd), 0.02);
  if Z > max then Z = max;
  else if Z < min then Z = min;
  base = Z;
end;
run;

```

where

- trt = treatment group coded as 1 for the test IOL and 2 for the control IOL
- base = BCDVA at baseline
- aval\_vi = BCDVA at Visit i, i = 2, 3, 4, and 5.

Similar code as above will be used for DCNVA with "base" replace by "aval\_v3" in the means procedure block of code and the data step cmiss if-condition updated to "if cmiss(aval\_v3, aval\_v4, aval\_v5) = 3" and clause "base = Z" updated to "aval\_v3 = Z".

Non-monotone missing data for BCDVA will first be multiply imputed using treatment-based MCMC methodology similarly as in the SAS® code below:

```

/* Impute non-monotone missing data using treatment-based MCMC

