for the first operative eye*/
proc mi data = indata out = mcmc nimpute = 30 seed = 891567 round
= 0.02;
  by trt;
  mcmc impute = monotone;
  var base aval_v2 aval_v3 aval_v4 aval_v5;
run;

```

Similar code as above will be used for DCNVA with the variables in the var statement updated to "aval\_v3 aval\_v4 aval\_v5".

Monotone missing data will be imputed for BCDVA using treatment-based re

BCDVA using SAS® code similar to the code below:

```
/* Treatment-based monotone regression imputation */
proc mi data = mcmc out = mi n impute = 1 seed = 891568 round =
0.02;
  by trt _imputation_;
  var base aval_v2 aval_v3 aval_v4 aval_v5;
  MONOTONE REG(aval_v2 = base);
  MONOTONE REG(aval_v3 = aval_v2 base);
  MONOTONE REG(aval_v4 = aval_v3 aval_v2 base);
  MONOTONE REG(aval_v5 = aval_v4 aval_v3 aval_v2 base);

run;
```

After imputation of non-monotone missing data, the DCNVA data will be partitioned into a dataset containing missing data due to withdrawal due to physician decision and a data set containing the remaining DCNVA data, including missing data due to any other reason:

```
/* Split mcmc into cases where missing is due to withdrawal due
to physician decision or other */
data mcmc1;
  set mcmc (where = (DSDECOD ne "Physician Decision"));
run;

data mcmc2;
  set mcmc (where = (DSDECOD = "Physician Decision"));
run;
```

where

- DSDECOD = reason for discontinuation.

The monotone missing data not due to withdrawal due to physician decision will be imputed using treatment-based regression methodology using SAS® code similar to the code below:

```
/* Impute missing data not due to Physician Decision using
treatment-based regression methodology */
proc sort data = mcmc1;
  by PARAMCD &trt. _imputation_;
run;

proc mi data = mcmc1 out = mil n impute = 1 seed = 891568 round =
0.02;
  by PARAMCD &trt. _Imputation_;
  var aval_v3 aval_v4 aval_v5;
  monotone reg(aval_v4 = aval_v3);
  monotone reg(aval_v5 = aval_v4 aval_v3);

run;
```

The resulting imputed data will then be combined with the missing data due to withdrawal due to physician decision. If there is any missing data due to withdrawal due to physician decision, it will be imputed using control-based regression methodology using SAS® code similar to the code below:

```

data mcmc2;
  set mil mcmc2;
run;

proc sort data = mcmc2;
  by _imputation_;
run;

/* Control-based monotone regression imputation */
proc mi data = mcmc out = mi nimpute = 1 seed = 891568 round =
0.02;
  by _imputation_;

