  class trt;
  var base aval_v3 aval_v4 aval_v5;
  MONOTONE REG(aval_v4 = aval_v3);
  MONOTONE REG(aval_v5 = aval_v4 aval_v3);
  MNAR MODEL(aval_v4 aval_v5 / MODELOBS=(trt= "2"));
run;

```

Thirty complete datasets will be generated from the above code.

A two-sample t-test will be performed for each imputed dataset and the results of the t-tests will be pooled using PROC MIANALYZE. SAS® code similar to the code below will be used to perform the primary analysis for each imputed dataset and then combine inferences across the imputed datasets:

```

proc sort data = mi;
  by _imputation_;
run;

ods output statistics = stat1(where = (Method ne
"Satterthwaite"));
proc ttest data = mi alpha = α
  by _imputation_;
  class trt;
  var aval_v4;
run;

proc sort data = stat1;
  by class _imputation_;
run;

ods output ParameterEstimates = pes;
proc mianalyze data = stat1 alpha = &alpha theta0 = &theta0;
  modeleffects Mean;
  stderr STDERR;
  by class;
run;

```

where

- $\&\alpha$ lpha = the significance level; 0.10 for BCDVA and 0.05 for DCNVA

- $\theta_0$  = the assumed difference in population means under the null hypothesis, 0.10 for BCDVA and 0 for DCNVA

After pooling the statistical analyses across the imputation datasets, the output dataset resulting from PROC MIANALYZE will contain means and standard errors for each treatment group and for the difference in treatment groups (test minus control), a CI for the treatment group difference (90% CI for BCDVA and 95% CI for DCNVA), and a two-sided p-value testing for whether the difference in treatment group means equals 0. These statistics from PROC MIANALYZE will comprise the primary effectiveness analyses for the primary effectiveness endpoints. If the upper confidence limit of the 90% confidence interval for the difference in treatment group means for BCDVA at Month 6 (Visit 4) is less than 0.1, then  $H_{0e}$  will be rejected in favor of  $H_{1e}$ , and the FINEVISION HP IOL will be considered to be statistically non-inferior to the AcrySof® SN60AT [REDACTED] IOL in BCDVA. If the two-sided p-value < 0.05 in favor of FINEVISION HP IOL for DCNVA at Month 6 (Visit 4), then the FINEVISION HP IOL will be considered to be statistically superior to the AcrySof® SN60AT [REDACTED] IOL in DCNVA.

The study will be considered a success only if both primary effectiveness endpoints are met.

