### 13.2 Secondary Analyses

The secondary effectiveness endpoint is:

- Photopic monocular logMAR intermediate (66 cm) visual acuity with distance correction (DCIVA) in first operative eyes at Month 6 (Visit 4)

The secondary effectiveness endpoint will be based on the AAS. The primary analysis for DCNVA will be repeated for photopic DCIVA (66 cm) in first operative eyes at Month 6 (Visit 4). If the two-sided p-value < 0.05 in favor of FINEVISION HP IOL for DCIVA, then the FINEVISION HP IOL will be considered to be statistically superior to the AcrySof® SN60AT [REDACTED] IOL in DCIVA.

Inference will be conducted for the secondary effectiveness analysis only if all primary effectiveness endpoints are met.

The sensitivity analyses for DCNVA will also be repeated for photopic DCIVA (66 cm) in first operative eyes at Month 6 (Visit 4).

Subgroup and poolability analyses of photopic monocular DCIVA (66 cm) in first operative eyes from the AAS at Month 6 (Visit 4) will be performed similarly as those for DCNVA.

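### With 2:1 allocation, the SAP code tests BCDVA, DCNVA and DCIVA with the equal-variance standard error, so test size and interval coverage depend on an unsupported assumption

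*SAP*

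**What the plan says.** SAP 13.1 sets out the primary analysis of BCDVA and DCNVA: "A two-sample t-test will be performed for each imputed dataset and the results of the t-tests will be pooled using PROC MIANALYZE". In the code, the statement "ods output statistics = stat1(where = (Method ne" goes on to name Satterthwaite as the method to leave out. PROC TTEST reports the difference in means by two methods, Pooled and Satterthwaite. The difference row that survives is therefore the pooled, equal-variance one, and its mean and standard error go to PROC MIANALYZE. The SAP makes that output the primary effectiveness result. SAP 13.2 repeats the DCNVA analysis for DCIVA.

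Protocol 9.4.3 and 9.4.4 ask for a two-sample t-test and, for BCDVA, a t-distribution interval; neither section says whether variances are taken as equal. Equal variances otherwise appear only in the sample-size text: "a common standard deviation (SD) of 0.10 logMAR" for BCDVA (SAP 5.1.1), and "with a common standard deviation of 0.14 logMAR" for DCNVA and DCIVA (Protocol 9.2).

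The treatment-based imputation steps in SAP 13.1 run separately by arm. The initial draw for eyes with no data uses an "SD equal to the respective treatment group SD based on observed data for the respective treatment group". Sensitivity Analyses I to III (SAP 13.1.1 to 13.1.3) change the imputation or the analysis set and keep the same test.

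**The concern.** The equal-variance t-test is robust to unequal SDs when the arms are the same size. It is not robust at 2:1. The pooled variance is weighted towards the larger arm, while the true variance of the difference is driven more by the smaller one. If the control arm (about 150 eyes) is more variable, the standard error is too small, the test is liberal and the interval too narrow. If it is less variable, the reverse holds.

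A trifocal is being compared with a monofocal lens, and nothing in the documents supports equal spread of near, intermediate or distance acuity in the two arms. The imputation steps that work by arm let the variances differ; the test then imposes a common one. At stake are the size of the three confirmatory effectiveness tests and the coverage of the reported 90% and 95% intervals. Requiring both co-primary tests to succeed does not restore nominal size: it bounds the chance of false study success only at the larger of the two individual sizes.

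A secondary point is that the test also omits site, the randomisation stratum (Protocol 6.3, SAP 4.4). That omission is usually conservative if arms are balanced within site, sites are prognostic and the effect is common across sites.

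**Working it through.** **Inputs.** 300 test and 150 control eyes completing, from 334 and 167 operated with 10% loss (SAP 5). BCDVA: one-sided 5%, SD 0.10, margin 0.10, true difference 0 (SAP 5.1.1). DCNVA and DCIVA: two-sided 5%, difference -0.10, SD 0.14 (SAP 5.1.2, 5.3.1). The documents give no arm-specific SDs, so every SD ratio below is an assumption.

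**Stated power reproduces.** sqrt(1/300 + 1/150) = 0.10.
- BCDVA: SE = 0.10 × 0.10 = 0.0100; 0.10/0.0100 = 10.0 standard errors; power about 1.000.
- DCNVA and DCIVA: SE = 0.14 × 0.10 = 0.0140; 0.10/0.0140 = 7.14 standard errors; power 0.9999999.

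Both agree with the stated figure of more than 99%.

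**Size of the equal-variance test.** Let s1, s2 be the test and control SDs and n1, n2 the arm sizes.

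R = pooled SE / true SE = sqrt{ [((n1-1)s1² + (n2-1)s2²)/(n1+n2-2)] × (1/n1 + 1/n2) / (s1²/n1 + s2²/n2) }

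Two-sided size = 2·P(Z > 1.96R). BCDVA size = P(Z > 1.645R). 90% coverage = 1 - 2 × the BCDVA size.

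Example with 0.08/0.12 (test/control): pooled variance = (299 × 0.0064 + 149 × 0.0144)/448 = 0.00906, so pooled SE = sqrt(0.00906 × 0.01) = 0.00952. True SE = sqrt(0.0064/300 + 0.0144/150) = 0.01083. R = 0.879.

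| Control/test SD | R | Two-sided size (5%) | Favouring test lens (2.5%) | BCDVA size (5%) | BCDVA 90% coverage |
|---|---|---|---|---|---|
| 1.5 | 0.879 | 8.5% | 4.2% | 7.4% | 85.2% |
| 1.25 | 0.929 | 6.9% | 3.4% | 6.3% | 87.4% |
| 1.2 | 0.941 | 6.5% | 3.3% | 6.1% | 87.8% |
| 1.0 | 1.000 | 5.0% | 2.5% | 5.0% | 90.0% |
| 0.8 | 1.076 | 3.5% | 1.7% | 3.8% | 92.3% |
| 0.67 | 1.138 | 2.6% | 1.3% | 3.1% | 93.9% |

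Simulation of 200,000 normal trials per ratio at 300/150 agrees to within about 0.1 percentage point. With the Satterthwaite row, size was 4.9% to 5.1% at every SD ratio from 0.5 to 2. At 225/225 the equal-variance test has size 5.0% at every ratio tried, so the dependence comes from the 2:1 split.

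**With imputation.** 12,000 trials per row; 334/167 eyes; 10% of Visit 4 values missing completely at random; imputation by arm from Visit 3 (assumed correlation 0.5); values rounded to 0.02; 30 imputations; Rubin pooling. Monte Carlo SE is about 0.1 to 0.25 points.

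| Test | SD test/control | Pooled row | Satterthwaite row |
|---|---|---|---|
| Superiority, favouring test lens (2.5%) | 0.12/0.18 | 4.0% | 2.5% |
| | 0.14/0.18 | 3.4% | 2.6% |
| | 0.14/0.14 | 2.3% | 2.3% |
| | 0.18/0.12 | 1.2% | 2.4% |
| BCDVA, one-sided (5%) | 0.08/0.12 | 7.1% | 5.3% |
| | 0.10/0.12 | 6.1% | 4.9% |
| | 0.10/0.10 | 5.1% | 5.0% |
| | 0.12/0.08 | 3.5% | 5.3% |

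**Interval width at 300/150.** The BCDVA 90% half-width at 0.08/0.12 is 0.0157 pooled and 0.0179 Satterthwaite. The largest observed difference that still passes is then 0.10 - 0.0157 = 0.0843 against 0.10 - 0.0179 = 0.0821, a shift of about 0.002 logMAR. At 0.12/0.08 the two half-widths swap. The DCNVA 95% half-width at 0.12/0.18 is 0.028 against 0.032.

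**Power with Satterthwaite.** For a -0.10 difference with SDs 0.14/0.21 the SE is 0.01896 and power 99.95%. For BCDVA at 0.10/0.20, power is still above 99.9%.

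**The case against.** The strongest reply is that nothing turns on this. The planned effects lie 7 to 10 standard errors from the null or the margin, the BCDVA threshold moves by about 0.002 against a margin of 0.10, and no stated power figure is wrong. The SD ratios are assumed, the direction is unknown, and the test could as well be conservative. A prespecified equal-variance t-test is a legitimate two-sample t-test, matches the planning assumption and fits the protocol wording. Imputing by arm follows from the missing-data strategy and is not a statement about variances. By-arm means and standard errors will be in the output, so a reader could come close to the unequal-variance standard error. The code is described only as similar to what will be run. The simulation uses one missingness mechanism and one correlation, and omits the control-based step for physician-decision withdrawals.

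Most of this stands and sets the low weight of the point. It is also fair that the 8.5% figure counts rejections favouring the control lens; 4.2% against 2.5% is the relevant comparison. But by-arm standard errors in a table do not alter which row decides success or which interval is reported. That the code is only indicative is a reason to name the variance assumption in the text. The site omission has no demonstrated harm and does not affect the main point.

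**Conclusion.** The point holds, as an inexpensive improvement and not as a threat to the trial. The code makes the equal-variance standard error decisive for all three confirmatory effectiveness tests, and the only support is a common planning SD. If the control SD is between 0.67 and 1.5 times the test SD (an assumed range), false superiority for the test lens runs from about 1.3% to 4.2% and BCDVA size from 3.1% to 7.4%. Imputation leaves the pattern in place, slightly weakened. With equal SDs there is no problem. The algebra is certain; whether the SDs differ in this trial, and in which direction, cannot be known from the documents. At the planned effects the pass or fail result is unlikely to change; what is gained is correct size and interval coverage whatever the arm variances turn out to be.

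**What to change.** In the PROC TTEST output filter of SAP 13.1, exclude the Pooled row instead of the Satterthwaite row, so that the unequal-variance standard error goes to PROC MIANALYZE for BCDVA, DCNVA and, through 13.2, DCIVA. The per-arm rows are still kept. State in the SAP text that the t-test does not assume equal variances. Keep the 90% and 95% intervals and the decision rules as they are.

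The cost is one word of code and one sentence in an SAP revision, best made before unmasking. The analysis remains a two-sample t-test with a t-distribution interval, as the protocol requires, and study conduct is untouched. Intervals will be wider if the control arm is more variable and narrower if it is less variable.

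A supportive model with treatment and site is optional and separate. It would need arm-specific or robust variance, a rule for small sites that excludes no eye (a random site intercept, for example), and imputation models that also include site. That means additional SAP text and code, and the main fix does not depend on it.

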#### 9.4.3 ANALYSIS OF PRIMARY EFFECTIVENESS ENDPOINTS

The statistical analyses described in ISO 11979-7, ISO 11979-9, and ANSI Z80.12 will be performed unless otherwise specified in the statistical analysis plan.

The co-primary effectiveness endpoints are:

- Photopic monocular logMAR best corrected distance visual acuity (BCDVA) in first operative eyes at Month 6 (Visit 4)
- Photopic monocular logMAR distance corrected near visual acuity (DCNVA) in first operative eyes at Month 6 (Visit 4)

Primary effectiveness endpoint analyses will be based on the All-implanted Analysis Set. Imputation of missing data will be performed utilizing multiple imputation techniques under assumptions of missing at random and missing not at random following the primary strategy presented in Section 9.4.2. As sensitivity analyses, the primary effectiveness analyses will be repeated using the secondary multiple imputation strategies presented in Section 9.4.2, as well as on the ITT and Best Case Sets using the primary multiple imputation strategy only. If the results of the ITT or Best Case Set robustness analyses materially differ from the primary analyses on the All-implanted Analysis Set then the results of investigations into the cause of such differences will be presented.

Photopic monocular BCDVA in first operative eyes at Postoperative Month 6 (Visit 4) will be primarily summarized using continuous summary statistics by treatment group. The treatment effect [mean Test group IOL visual acuity (VA) minus mean Control group IOL VA] in logMAR units will be presented in addition to a two-sided 90% t-distribution confidence interval around the difference. If the upper confidence limit is less than 0.1, then  $H_{01e}$  will be rejected in favor of  $H_{11e}$  and the FINEVISION HP IOL will be considered to be statistically non-inferior to the AcrySof SN60AT [REDACTED] IOL in BCDVA.

Photopic monocular DCNVA in first operative eyes at Postoperative Month 6 (Visit 4) will be summarized using continuous summary statistics in logMAR units by treatment group. The FINEVISION HP IOL will be compared to the AcrySof SN60AT [REDACTED] IOL using a two-sample t-test with a two-sided alpha of 0.05. If the two-sided p-value < 0.05 in favor of FINEVISION HP IOL for DCNVA, then the FINEVISION HP IOL will be considered to be statistically superior to the AcrySof SN60AT [REDACTED] IOL in DCNVA.

The study will be considered a success only if both primary effectiveness endpoints are met.

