#### 9.4.4 ANALYSIS OF SECONDARY EFFECTIVENESS ENDPOINTS

The secondary effectiveness endpoint is:

- Photopic monocular logMAR DCIVA at 66 cm in first operative eyes at Month 6 (Visit 4)

The secondary effectiveness endpoint will be based on the All-implanted Analysis Set. Imputation of missing data and sensitivity analyses for the secondary effectiveness endpoint will be performed similarly as for the primary effectiveness endpoints.

Photopic DCIVA (66 cm) in first operative eyes at Postoperative Month 6 (Visit 4) will be summarized using continuous summary statistics in logMAR units by treatment group. The FINEVISION HP IOL will be compared to the AcrySof SN60AT [REDACTED] IOL using a two-sample t-test with a two-sided alpha of 0.05. If the two-sided p-value < 0.05 in favor of FINEVISION HP IOL for DCIVA, then the FINEVISION HP IOL will be considered to be statistically superior to the AcrySof SN60AT [REDACTED] IOL in DCIVA.

Inference will be conducted for the secondary effectiveness analysis only if all primary effectiveness endpoints are met.

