#### **4.3 Study Treatments**

#### **4.4 Method of Assigning Subjects to Treatment Groups**

During the Pre-Operative Visit, subjects who sign the informed consent form will be assigned a unique 4-digit screening number, where the first two digits correspond to the site number. Subjects who meet eligibility criteria for cataract surgery/IOL implantation will be randomized in a 2:1 ratio to receive either the FINEVISION HP (Test) IOL or the AcrySof® SN60AT [REDACTED] Control) IOL in both eyes according to the randomization schedule. Randomization will be stratified by site. The randomization schedule will be created using computer-generated randomization methodology ([REDACTED] [REDACTED]) by an independent statistician who is not involved in the day-to-day conduct of the study. Randomization is to occur following the completion of informed consent and screening procedures.

The 4-digit subject ID will be used to identify subjects in all datasets and listings for this study.

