#### **7.5 [REDACTED]**

### **8. General Statistical Considerations**

#### **8.1 Unit of Analysis**

The unit of analysis in this study will be the first operative eye for all primary effectiveness and safety summaries, and the unit of analysis will be the second operative eye and all eyes for supportive safety summaries; [REDACTED]

[REDACTED]. Both eyes of each subject will be treated during the study. For those subjects whose eyes are both determined to be eligible for cataract surgery/IOL implantations at Pre-Operative Visit 0, the eye with the worse BCDVA will be scheduled for surgery first. If BCDVA is the same for both eyes, the right eye will be implanted first. Additionally, non-ocular AEs and medical history will be presented at the subject level.

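### BCDVA, DCNVA and DCIVA are tested without site or preoperative BCDVA; adjusting for both could narrow the intervals slightly and needs no new data (low priority)

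*SAP*

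**What the plan says.** **Tests.** SAP 13.1: "A two-sample t-test will be performed for each imputed dataset and the results of the t-tests will be pooled using PROC MIANALYZE". The code is PROC TTEST with treatment as the only class variable. SAP 13.2 repeats the DCNVA analysis for DCIVA. Protocol 9.4.3 gives BCDVA a 90% t-distribution interval with no covariates and compares DCNVA "using a two-sample t-test with a two-sided alpha of 0.05". Protocol 9.4.4 does the same for DCIVA.

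**Randomisation.** SAP 4.4: "Randomization will be stratified by site". Protocol 6.3 agrees.

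**Preoperative BCDVA.** It is measured at Visit 0, which SAP 8.3 defines as baseline. In the effectiveness analyses it serves only as a predictor in the BCDVA imputation, where "base = BCDVA at baseline". Outside those analyses it picks the first operative eye, since "the eye with the worse BCDVA will be scheduled for surgery first" (SAP 8.1), and it enters the change-from-baseline summaries in SAP 16.1. For the DCNVA imputation, SAP 13.1 says "Similar code as above will be used for DCNVA with the variables in the var statement updated to" the Month 1, 6 and 12 values. The control-based DCNVA block does list the baseline variable in its VAR statement, but neither regression in that block uses it.

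**Site.** It enters an effectiveness model only in the poolability analysis (SAP 13.1.5). The readable text gives no covariate-adjusted analysis of the three endpoints and no reason for leaving one out.

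**The concern.** When randomisation is stratified, the stratum is a natural term for the analysis model, and a baseline acuity already in hand is a natural covariate. If either is prognostic, a treatment-only t-test leaves explainable variation in its standard error and the interval is wider than it need be. If the arms are also balanced within site, the unadjusted test becomes slightly conservative.

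The poolability model does not fill the gap. It uses observed rather than imputed data, omits sites with fewer than 6 subjects and includes the site-by-treatment interaction. Its code keeps site-effect tests, treatment-by-site means and within-site differences. No overall site-adjusted lens effect comes out.

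What is at stake is the width of the reported intervals, not the validity of the conclusions.

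**Working it through.** **Inputs from the documents** (protocol 9.2; SAP 5 to 5.3): 300 test and 150 control eyes; SD 0.10 logMAR, margin 0.10 and true difference 0 for BCDVA (one-sided 0.05); SD 0.14 and true difference -0.10 for DCNVA and DCIVA (two-sided 0.05); up to 24 sites.

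**Assumed, because the documents give no figures:** site ICC 0 to 0.10; within-site correlation r of preoperative with Month 6 BCDVA 0 to 0.4.

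**1. The plan's own power.** SE = SD × √(1/300 + 1/150), which is 0.0100 for BCDVA and 0.0140 for DCNVA and DCIVA. The noncentrality is 0.10/0.0100 = 10.0 and 0.10/0.0140 = 7.14. Power exceeds 99.99% in both cases, so the stated >99% is reproduced without adjustment.

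**2. Unadjusted half-widths (448 df).** BCDVA 90%: 1.648 × 0.0100 = 0.0165. DCNVA and DCIVA 95%: 1.965 × 0.0140 = 0.0275.

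**3. Effect of adjustment.** With arms balanced within site, the width is multiplied by √((1 − ICC)(1 − r²)). This was checked by simulation for BCDVA: 12,000 trials per scenario, 501 randomised, 24 sites of assumed size 4 to 60, 10% random loss, random site intercept plus baseline, and site dropped when its variance was estimated as zero. There was no imputation step. Balanced runs assumed blocks of 3 within site; the others allocated 2:1 independently.

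| ICC, r | Formula, balanced | Simulated, balanced | Simulated, no balance |
|---|---|---|---|
| 0, 0 | 1.000 | 0.999 | 1.000 |
| 0.02, 0.2 | 0.970 | 0.972 | 0.977 |
| 0.05, 0.2 | 0.955 | 0.959 | 0.968 |
| 0.10, 0 | 0.949 | 0.955 | 0.967 |
| 0.10, 0.4 | 0.870 | 0.875 | 0.888 |

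**4. In logMAR.**
- BCDVA, middle case: 0.0165 × 0.030 = 0.0005 balanced; 0.0165 × 0.023 = 0.0004 without balance.
- BCDVA, top of the range: 0.0165 × 0.130 = 0.0021 balanced (0.0022 before rounding); 0.0165 × 0.112 = 0.0018 without balance.
- DCNVA and DCIVA from site alone, at ICC 0.10: 0.0275 × 0.051 = 0.0014 balanced; 0.0275 × 0.033 = 0.0009 without balance.

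SAP 16.1 equates 0.20 logMAR with 10 letters, so one letter is 0.02. The largest BCDVA gain is then 0.0022/0.02 = 0.11 letter, or 2.2% of the margin.

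**5. Error rate.** Under balance the unadjusted one-sided level is 1 − Φ(1.645/√(1 − ICC)): 5.0, 4.8, 4.6 and 4.1% at ICC 0, 0.02, 0.05 and 0.10. Without balance it was 4.8 to 5.1% in simulation. Coverage of the adjusted 90% interval was 89.7 to 90.2% in all ten runs.

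**6. A less favourable truth.** With a true BCDVA difference of 0.07, power is 91.2% unadjusted, 92.4% if the covariates explain 5% of the variance and 93.5% if they explain 10%. The middle case explains 1 − 0.98 × 0.96 = 5.9%.

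**The case against.** The strongest reply is that this changes nothing. Power is already above 99%, the sample size comes from the ANSI minimum of 300 and 150, and the largest gain is about a ninth of a letter. A simple, valid, consistently specified test would give way to a more complex one for a benefit the documents cannot confirm. The baseline covariate may well be weak: acuity is measured through the cataract, and protocol 5.1 requires a projected postoperative BCDVA of 0.2 logMAR or better. DCNVA and DCIVA have no preoperative measurement of their own. The larger ranges assume within-site balance, yet the description of the randomisation method in SAP 4.4 is partly redacted. The simulation also did not include imputation and pooling.

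All of this stands, and it limits the point to low priority. It does not remove it: both covariates are already recorded, one is the randomisation stratum, and a prespecified adjustment leaves the decision rules as they are.

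A reader might infer more in three ways, and the documents support none of them:
- **That omitting the stratum invalidates the tests or inflates the type I error.** The treatment-only test is at or slightly below its nominal level.
- **That a definite gain is being lost.** The gain depends on an ICC and a correlation that are not given; at zero for both, the width changes by about 0.1%.
- **That the unused baseline variable in the DCNVA imputation code shows an intended adjustment.** It is in no regression there and says nothing about the precision of the test.

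**Conclusion.** The point holds as a small, optional gain in precision. The three confirmatory comparisons use neither the randomisation stratum nor the available baseline acuity, and no other planned analysis gives an overall adjusted effect. At ICC 0.02 and r 0.2 the BCDVA half-width would fall by about 3% with within-site balance and about 2% without. Over the full assumed range the fall is 0-13% or 0-11% for BCDVA, and 0-5% or 0-3% for DCNVA and DCIVA from site alone. These figures rest on the assumed ICC and correlation, on the planning SDs and on 300 and 150 evaluable eyes. The existing tests are valid, and no success conclusion is expected to change at the planning assumptions.

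**What to change.** Before unmasking, prespecify for each imputed dataset one linear model with treatment, a random site intercept and preoperative BCDVA of the first operative eye, and state the degrees-of-freedom method. The random intercept keeps small sites in the analysis, and a site variance estimated at zero simply drops out, so no separate fallback model is needed. Pool the adjusted test-minus-control difference and its SE in PROC MIANALYZE. Keep the decision rules: 90% upper limit below 0.10 for BCDVA, and two-sided p < 0.05 in favour of the test lens for DCNVA and DCIVA. Report the t-test as supportive.

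For consistency with that model, include preoperative BCDVA as a predictor in the DCNVA and DCIVA imputation regressions. No separate precision gain is claimed for this step.

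**Cost.** Wording and code in SAP 13.1 and 13.2, matching text in protocol 9.4.3 and 9.4.4, and an entry in SAP 19 if the protocol is not amended. No new data or subjects are needed. If site matters little, its term will often do nothing: the simulated site variance was zero in 55% of datasets at ICC 0 and in 17% at ICC 0.02.
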